opportunity to identify individuals in need and direct them toward long-term treatment programs. The current standard of care for individuals with OUD presenting to the ED provides management of acute symptoms and contact information for treatment programs, which often have long waiting lists.³ Here, we will compare the standard practice with a novel intervention that will provide 1) immediate initiation of buprenorphine treatment at the ED and 2) guaranteed placement in a specialized OUD treatment program (i.e. UVMMC Addiction Treatment Program -ATP) within 24 to 72 hours after discharge. The primary outcome measure will be opioid use at 1 week and 3 & 6 months after buprenorphine initiation.

Aim 1. To determine whether ED-initiated buprenorphine treatment coupled with enrollment in a bridge clinic that will supervise MAT until the patient is stabilized and placed with a local MAT provider will reduce illicit opioid use compared to ED-initiated buprenorphine treatment coupled with immediate referral to a local MAT provider.

Hypothesis: Patients assigned to the ED-initiated buprenorphine plus ATP bridge clinic intervention will have significantly reduced illicit opioid use as determined by urine drug screen at 1 week, and 3 & 6 months than patients who only receive direct referral to a local MAT provider. .

PURPOSE AND OBJECTIVES

Purpose: *The importance of the research and the potential knowledge to be gained should be explained in detail. Give background information.*

The explosive increase in opioid use in the U.S. over the past two decades poses a formidable threat to the national welfare.¹⁰⁻¹³ In the last month, an estimated 400,000 individuals have used heroin and over four million individuals have used prescription pain medication for non-medical purposes.^{14,15} The latest estimates released by the CDC for the year 2016 indicate that a dramatic surge in opioid related deaths has produced a population level decline in average life expectancy.¹⁶ Opioid-related overdose fatalities have quadrupled since 1999.¹ In 2016 alone, 63,200 Americans died of an opioid-related overdose, which represents a 21% increase over the preceding year. The rapid development of evidence-based approaches to manage the opioid epidemic is critical at this time. Here, we will examine whether an ED-initiated intervention will lead to lower rates of opioid use and higher enrollment in medical treatment for OUD.

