Objectives: Clearly state the primary and secondary objective(s) of the study.

The primary outcome will be urine specimens for illicit opioids at 1 week and 3 & 6 months after ED initiated treatment. Urine specimens will be collected under observation of same-sex staff and immediately analyzed for opioids (buprenorphine, methadone, oxycodone, hydrocodone, hydromorphone, heroin, fentanyl) and other drugs (cocaine, amphetamines, benzodiazepines, cannabinoids) via enzyme multiplied immunoassay. Missing urine specimens will be considered positive for illicit opioids, consistent with an intent-to-treat approach.

[figure not shown]
Secondary outcomes will include self-reported illicit opioid or other (non-opioid) drug use, treatment enrollment status and behavioral questionnaires (i.e. the GPRA Client Outcome Measures questionnaire, the Treatment Effectiveness Assessment (TEA),⁴³ and the Vermont Treatment Needs Questionnaire (TNQ)²¹).

METHODS AND PROCEDURES

Study Design: Describe the research design, including a description of any new methodology and its advantage over existing methodologies.

This pilot project will test whether ED-initiated buprenorphine treatment for individuals presenting to the UVMMC ED with OUD combined with a MAT bridge clinic leads to a reduction in illicit opioid use at 1 week, and 3 & 6 months compared ED-initiated treatment with a direct referral to a local MAT provider. The intervention and study design include 5 main stages (see figure below): 1) Patients admitted to the ED with indicators of OUD will be consented and screened for study eligibility; 2) Participants will undergo buprenorphine induction at the ED; 4) Participants enrolled at Central Vermont Medical Center and Porter Medical Center will be referred directly to a local MAT provider. Participants enrolled at UVMMC will be referred to the UVMMC ATP, a MAT bridge clinic that will supervise MAT with buprenorphine in all participants who enroll in the program until the individual is transferred to a long-term MAT provider, referred to a higher level of care or drops out of treatment --treatment duration at ATP is typically 8 weeks before referral of stable patients to primary care providers; 5) All participants will be contacted at 1 week, and 3 & 6 months after randomization to determine current illicit opioid use.

We expect to enroll 200 participants over 3 years.

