Procedures: Describe all procedures (sequentially) to which human participants will be subjected. Identify all procedures that are considered experimental and/or procedures performed exclusively for research purposes. Describe the types, frequency and duration of tests, study visits, interviews, questionnaires, etc. Include required screening procedures performed before enrollment and while on study. Please provide in table, list or outline format for ease of review. (describe and attach all instruments)

Note: A clinical research protocol may involve interventions that are strictly experimental or it may involve some aspect of research (e.g., randomization among standard treatments for collection and analysis of routine clinical data for research purposes). It is important for this section to distinguish between interventions that are experimental and/or carried out for research purposes versus those procedures that are considered standard therapy. In addition, routine procedures performed solely for research purposes (e.g., additional diagnostic/follow-up tests) should be identified.

Our project team (Drs. [name], [name], [name] and [name]) includes clinical and research expertise required to undertake the study. [name] is an addiction psychiatrist who heads the UVMMC ATP and [name] is clinical research faculty. Drs. [name] and [name] are UVMMC ED physicians. [name], RN and [name], LCMHC, LADC will coordinate research support at the ED Research Program and ATP, respectively.

The study consists of 4 parts: 1) Recruitment, 2) Buprenorphine Induction, 3) Referral, and 4) Outcome Assessment at 1, 3, and 6 months.

Recruitment, Randomization and Buprenorphine Induction or Referral all occur during the initial visit to the ED. The part of the protocol performed at the ED can be summarized in 11 steps. See also illustration of EMRAP staff structure in Informed Consent section.

Brief Summary Table Listing 11 Steps During Initial ED Visit

1. Recruitment

Step 1. Patients arrive at Emergency Department.

Identification

Step 2. Research Associates (EMRAP undergrad trainees) identify potential participants based on indicators of OUD in EPIC Electronic Health Records (EHR).

Step 3. Research Associates will notify an EMRAP Research Coordinator of potentially eligible participants. The Research Coordinators are full-time EMRAP research employees.

Prescreening

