Step 4 Research Coordinator will confirm in-person or via telephone with ED physicians/nurses providing care for patient that approaching the individual is appropriate and will not interfere with service.

Step 5 Research Associate or Research Coordinator approaches potential participant and performs prescreen either in-person or via telephone. The prescreen text is attached to this application. Prescreening information is stored in REDCap. If a subject is found to be ineligible, data entered for that subject will be deleted from REDCap at that time.

Step 6 Based on answers consistent with opioid use disorder, proceed to next step otherwise thank individual and destroy prescreen answers.

Step 7 If patient declines continuing enrollment process, will be provided with informational wallet card describing research study, informing patients that they may return to the ED at a later date to reattempt enrollment

Consenting

Step 8 Participant is consented into the study by one of the Research Coordinators either in person or via telephone with coordination from ED care team to sign appropriate documentation. If eligible participant does not consent, individual will be thanked and prescreen information destroyed. Prescreening information is stored in REDCap. If a subject is found to be ineligible, data entered for that subject will be deleted from REDCap at that time. Consent may be completed via eConsent form. Printed copy of signed consent form will be provided to the consent after completing consent process.

Step 9 Research Coordinator confirms OUD diagnosis.

2. Buprenorphine Induction

Step 10 Participants receive induction treatment from ED physician who has been certified to prescribe Suboxone.

3. Referral

Step 11 Participants enrolled at Central Vermont Medical Center or Porter Medical Center are referred to a local MAT provider. Participants enrolled at UVMMC are referred to the UVMMC ATP, a MAT bridge clinic.

Step 12 Research Associate leads participant through behavioral questionnaire battery on ipad. (This step may occur before step 10 while the participant is waiting to see ED physician).

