Follow up questionnaire (attached) based on PhenX drug use history toolkit takes approximately 105 minutes to complete TEA takes approximately 5 minutes to complete

The GPRA Client Outcome Measures questionnaire takes approximately 30 minutes to complete.

Baseline questionnaires will be administered on an iPad by the EMRAP staff or the study RA in patient care areas or by phone.

At 1 week, 3 months and 6 months, questionnaires will be administered by the study RA by phone. Participants may be contacted in advance by text or email to arrange a time for the call that is convenient for the participant.

Questionnaires will be labelled with the participant's unique study ID number and stored separately from identifiable information (e.g. name, address, phone number etc).

Statistical Considerations: Delineate the precise outcomes to be measured and analyzed. Describe how these results will be measured and statistically analyzed. Delineate methods used to estimate the required number of subjects. Describe power calculations if the study involves comparisons. Perform this analysis on each of the primary and secondary objectives, if possible.

200 hundred individuals will be recruited to the study over the course of 3 years.

The primary outcome measure will be illicit opioid use at 1 week and 3 & 6 months.. Group differences (i.e. with or without the MAT bridge clinic) in opioid use will be assessed by logistic regression at each of the three time points. A power analysis using G*Power50 indicates that a medium effect size, e.g. 0.3, related to the comparison of illicit opioid use in the experimental and control groups will be correctly identified with a power of 0.93 in a total sample of 200 individuals. Statistical tests will be performed in SPSS Statistics for Windows, Version 21.0. (Armonk, NY: IBM Corp). Logistic regression will be one-tailed with significance defined as $p < 0.05$.

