Clinical support for withdrawal will be provided by addiction psychiatrists at the ATP. Participants who receive ED-initiated buprenorphine treatment are guaranteed placement in the ATP. The ATP team includes two fellowship-trained addiction psychiatrists, one general psychiatrist, and one family

physician who are all experienced in treating OUD, as well as resident and fellow trainees from psychiatry, family medicine, and internal medicine, and licensed professionals in nursing, alcohol and drug counseling, mental health counseling and clinical social work. The staff is experienced in providing MAT to patients in all phases of treatment, in diverse settings and across levels of acuity, as well as in educating, training and supporting colleagues with varying levels of experience, training and comfort in addictions treatment. The ATP was selected by the State of Vermont to lead a state-wide Learning Collaborative Project to provide training and education to MAT practices throughout the state of Vermont.

Participant data will be coded to protect privacy. Each patient will be assigned a unique identification number. The list of participant names and identification numbers will be kept in a locked file cabinet separate from the database. Access to the computerized data system is carefully protected by a secured password entry system. Participants will be made aware of the various parties who will have access to their data in the informed consent document. Access to participants' data will be restricted to project investigators and other study staff on a need to know basis. Patient information, if reported, will be reported as group data. No patients will be individually identified.

To minimize risk of divulging confidential information regarding substance use or other illegal activities as well as other study information, strict attention to confidentiality will be maintained throughout every aspect of this research with standard policies and procedures, and protected by a Certificate of Confidentiality issued by NIH.

Individuals from vulnerable populations will not be included in the study.

Incidental findings will be reported to the participant by a study MD.

Potential Benefits

Participants enrolled in the study will either receive standard of care or buprenorphine MAT, which is the most effective current treatment for the disorder. Participants will be provided guaranteed access to treatment by specialized addiction psychiatrists at the ATP.

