Subject Selection: *Provide rationale for subject selection in terms of the scientific objectives and proposed study design.*

Subjects will be screened for inclusion if they present to the ED with signs of opioid use disorder (i.e. self-report or symptoms consistent with the disorder) Symptoms consistent with the disorder include: presentation with acute overdose or symptoms consistent with opioid withdrawal (such as piloerection, diarrhea, tachycardia, cravings, and pupillary dilation), and EMS use of naloxone on scene or en route to the hospital, patients with abscesses, especially in the antecubital fossa and other areas consistent with injection drug use and patients with a history of endocarditis.

Vulnerable Populations: *Explain the rationale for involvement of special classes of subjects, if any. Discuss what procedures or practices will be used in the protocol to minimize their susceptibility to undue influences and unnecessary risk (physical, psychological, etc.).*

Not applicable

Number of Subjects: *What is the anticipated number of subjects to be enrolled at UVM/UVM Medical Center and in the case of a multi-center study, with UVM/UVM Medical Center as the lead, the total number of subjects for the entire study.*

We expect to enroll 140 participants at UVMMC and 200 participants in total.

Inclusion/Exclusion Criteria: Eligibility and ineligibility criteria should be specific. Describe how eligibility will be determined and by whom. Changes to the eligibility criteria at a later phase of the research have the potential to invalidate the research.

Inclusion Criteria:

- Present to the UVMMC Emergency Department (and later after IRB review the Emergency Departments at Central Vermont Medical Center and Porter Medical Center)
- Endorse criteria for Opioid Use Disorder (OUD) as defined by the DSM-V
- Over the age of 18

Exclusion Criteria:

- Non-english speaking
- Current participation in an alternate treatment program for OUD (except recent release from correctional facility or residential treatment program and does not have a current prescription),
- Inability to communicate
- Altered mental status
- Suicidality
- Medical extremis or medical issue requiring admission
- Prisoners
- History of Suboxone injection in the past year
- Hepatic impairment

Inclusion of Minorities and Women: Describe efforts to include minorities and women. If either minorities or women are excluded, include a justification for the exclusion.

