-Sex/gender will not be a selection/exclusion factor for the recruitment. In Vermont, women compose ~50% of the general population. Thus, we anticipate a similar proportion in the proposed research. However, participants will be recruited to the study because they present to the ED and are eligible. The predetermined randomization tables which include a stratification by sex will insure that equal numbers of women are sorted to the control and experimental groups.

Pregnant and nursing mothers will not be excluded. Opioids such as the buprenorphine contained in Suboxone can cause birth defects. However, opioid withdrawal can be especially harmful during pregnancy, potentially resulting in preterm labor, fetal distress, or even miscarriage. Buprenorphine reduces opioid craving and alleviates withdrawal symptoms without the safety and health risks related to acquiring and abusing street drugs. Treatment with Suboxone is considered to be a lower clinical risk to the fetus than uncontrolled use of illicit opioids. In contrast to earlier recommendations about buprenorphine+naloxone, recent research is consistent with Suboxone being as safe or safer than buprenorphine monotherapy during pregnancy. This pilot project will inform practical aspects of the network-wide implementation of an ED-initiated intervention for OUD in Vermont including patients who are pregnant.

-Minorities. There will be no exclusion criteria concerning race or ethnicity. In Vermont, minorities represent approximately 5% of the general population. Thus, we anticipate a similar proportion in the proposed study. We will do all that we can to assure that minorities are represented in the research.

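### Group is fixed by enrolling hospital and no listed step randomises anyone, yet the protocol promises sex-stratified randomisation tables and prespecifies no covariates for the group comparison

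*Combined protocol and SAP*

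**What the plan says.** **Allocation.** Step 11 of the ED summary table reads: "Participants enrolled at Central Vermont Medical Center or Porter Medical Center are referred to a local MAT provider". The same step sends UVMMC participants to the ATP bridge clinic. Study Design and the Referral section repeat the rule.

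**Randomisation.** The section on women and minorities says: "The predetermined randomization tables which include a stratification by sex will insure that equal numbers of women are sorted" to the control and experimental groups. Procedures says: "Recruitment, Randomization and Buprenorphine Induction or Referral all occur during the initial visit to the ED". Study Design says: "All participants will be contacted at 1 week, and 3 & 6 months after randomization to determine current illicit opioid use". Randomisation is also the time origin in Part 2 (follow-up dates and Step 11 data), in Part 5 (Retention and the contact paragraph) and in Payment for participation. No ratio, sequence generation or concealment is described.

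**Numbers.** Number of Subjects says: "We expect to enroll 140 participants at UVMMC and 200 participants in total". Women are expected to be about half.

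**Timing.** The note before Part 1, repeated under Collaborating Sites, says that the two control hospitals are not ready, asks for UVMMC to go on enrolling meanwhile, and leaves the other sites to later amendments.

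**Comparator.** Aim 1 gives both groups ED-initiated buprenorphine and contrasts bridge clinic with direct referral. The introduction says: "Here, we will compare the standard practice with a novel intervention that will provide" ED buprenorphine and guaranteed ATP placement. Protections Against Risks says: "Participants who receive ED-initiated buprenorphine treatment are guaranteed placement in the ATP". Data Safety and Monitoring likewise has participants on buprenorphine monitored at the ATP.

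**Analysis.** Statistical Considerations says: "Group differences (i.e. with or without the MAT bridge clinic) in opioid use will be assessed by logistic regression" at each of three time points, one-tailed at 0.05. It names no covariate, site term or sensitivity analysis.

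**The concern.** The current text describes two incompatible designs. A reader or ethics board relying on the randomisation sentence would take the groups to be comparable by design. Under the allocation rule they are not. The bridge-clinic group is a single hospital, so the group effect and the hospital effect cannot be separated, and a site term cannot be fitted alongside group. Patient mix, setting and calendar period can all contribute to the estimated effect.

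Not all of this is bias. Local treatment provision in the control areas is partly the comparator that Aim 1 intends. The rest matters because Impact and Potential Benefits say that positive findings will support adoption across the network.

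Two further points follow. The follow-up clock is tied in several places to an event that no step performs. And if the statements on ATP placement and monitoring apply to everyone given ED buprenorphine, then under Aim 1 they cover the controls too, which would erase the contrast being tested.

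**Working it through.** **1. Allocation and randomisation side by side.** The ED steps run from arrival through identification, prescreening, consent, OUD confirmation, induction, referral by hospital and questionnaires. None is a randomisation step. Three sections give the hospital rule; one promises randomisation tables; several others use randomisation as a time point. Both descriptions cannot be true.

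**2. Women.** Inputs: 140 at UVMMC, 200 in total, about 50% women.
- UVMMC: 0.5 × 140 = 70.
- Controls: 0.5 × (200 − 140) = 30.

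Equal numbers are not met by hospital allocation.

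**3. Hospital gap.** The documents give no positive-test rates, so these are assumptions: no true effect, 60% positive at UVMMC, 65% or 70% at the control hospitals for other reasons, 140 versus 60, one-sided 0.05, pooled z-test. The normal approximation is Φ[(gap − 1.645 × SE0)/SE1].
- 5 points: pooled rate = (140 × 0.60 + 60 × 0.65)/200 = 0.615. SE0 = √[0.615 × 0.385 × (1/140 + 1/60)] = 0.0751. SE1 = √(0.60 × 0.40/140 + 0.65 × 0.35/60) = 0.0742. Φ(−0.99) = 0.161; exact binomial enumeration gives 0.163.
- 10 points: pooled rate 0.630, SE0 = 0.0745, SE1 = 0.0722. Φ(−0.31) = 0.377; exact 0.384.
- For UVMMC rates of 40% to 80%, the exact ranges are 16–19% and 36–54%.
- With the gap reversed: 1.0% and 0.1%.
- Restricting to concurrent enrolment barely helps: 15% and 36% at 105 versus 60; 15% and 33% at 70 versus 60.

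**4. Measured patient mix.** Simulation, five-term logistic model, no true effect. Assumed: 50% of UVMMC and 70% of control participants inject, and injecting multiplies the odds of a positive test by 2 or 3.

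| Analysis | OR 2 | OR 3 |
|---|---|---|
| Unadjusted | 11% | 17% |
| Adjusted, route recorded correctly | 5% | 5% |
| Adjusted, 10% of routes misrecorded | 7% | 8% |
| Adjusted, 20% of routes misrecorded | 9% | 12% |

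These runs assume complete covariates.

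**5. Calendar period.** Assumed: early UVMMC participants are 10 points less often positive (50% versus 60%), later UVMMC and control participants are equal. With 25% or 50% of UVMMC enrolled early, false positives are 9% or 16% in the full comparison, and 5% after restriction if the change stops when the control hospitals open. If positivity instead rises linearly from 55% within the concurrent window (105 versus 60), restriction leaves:

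| Enrolment pattern | 10-point rise | 20-point rise |
|---|---|---|
| One control site opens halfway | 7% | 9% |
| UVMMC finishes in the first half | 9% | 15% |
| Both | 12% | 24% |

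**6. Cost in precision.** The standard error ratio of the restricted to the full analysis is √[(1/105 + 1/60)/(1/140 + 1/60)] = √1.10 = 1.05 if 25% of UVMMC enrols early, and √[(1/70 + 1/60)/(1/140 + 1/60)] = √1.30 = 1.14 if 50% does. Power for 40% versus 60% is 84% in all 200, and 80% or 74% in the restricted sets. The five-term adjusted model keeps about 84% when covariates are complete, balanced and unrelated to outcome.

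**The case against.** The strongest reply is that the randomisation wording is left over from another design: Study Design announces five stages but numbers them 1, 2, 4 and 5. Aim 1, Study Design and Step 11 state the comparator plainly. Control-site details are deferred to amendments, and while only UVMMC is open every participant does go to the ATP. The study is called a pilot. All of this is fair, and it means the comparator is not unknown. But the sentences stand in the current text and need correcting.

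Some stronger readings are tempting and are not supported:
- A reader might infer that the plan declares an unadjusted analysis or an unrandomised design. It says neither. No covariate is named, and the absence of randomisation follows from the hospital rule and the list of steps. The design figure is not available, but the text is explicit in three places.
- A reader might infer a sex imbalance. The expected share is 50% in both groups; only the promise of equal numbers fails.
- A reader might infer that restriction to concurrent enrolment cures calendar confounding, or that a period term should be ruled out. Step 5 of the check shows that drift within the window survives restriction.
- A particular covariate list is one reasonable choice, not a demonstrated necessity.

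Finally, every rate, gap and early share above is assumed. They show how sensitive the test is, not how much bias to expect.

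**Conclusion.** The protocol is wrong as written and must be corrected. Allocation by hospital contradicts the promised sex-stratified randomisation, and the only figure that follows from the plan's own numbers is about 70 versus 30 women where equal numbers are promised. Because hospital is completely aliased with group and no covariates are prespecified, differences in hospital, patient mix and calendar period enter the estimate. On the assumed rates, a 5- or 10-point hospital gap favouring UVMMC yields a false claim of benefit 16% or 38% of the time; a gap the other way would hide a benefit. No analysis removes the pure hospital part, so the label and the conclusion have to carry it. Measured patient mix can be largely adjusted for if it is well recorded, and calendar confounding can be reduced but not guaranteed away. The documents do not show that the result will be biased, or in which direction. This point does not rest on the plan's power figure.

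**What to change.** 1. **Design wording.** Unless individual randomisation is actually restored, delete the randomisation and sex-stratification statements wherever they occur and call the study a non-randomised hospital comparison. Use one follow-up origin throughout. At present randomisation, buprenorphine initiation (introduction), ED-initiated treatment (Objectives) and induction (Part 5) all appear, and some participants start buprenorphine at home. Reconcile the introduction, Protections Against Risks, Potential Benefits (which names standard of care as the alternative) and Data Safety and Monitoring with Aim 1 on what the comparator is and whether control participants have ATP access.
2. **Primary analysis.** In Statistical Considerations, prespecify adjustment for a short list of baseline variables already collected, for example age, sex, route and duration of opioid use. Keep all participants and state how missing history is handled. Opioid history may be taken by phone up to seven days later, so people who cannot be reached may lack it and also be scored positive for a missing urine. With four covariates plus group there are 80/5 = 16 negative results per term at 60% positive and 40/5 = 8 at 80%, so the list should stay short. Do not fit a site term.
3. **Sensitivity analysis.** Prespecify one restricted to participants enrolled while a control hospital is open. A calendar-time term within that window may be added. State that this reduces calendar confounding but does not remove it if sites open at different times or enrolment is not parallel.
4. **Conclusion.** Report a non-randomised association with residual hospital and calendar confounding, and limit the network-wide adoption statements in Impact and Potential Benefits to pilot evidence for further research.

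**Cost.** No new patients or visits. There is slightly more analysis, and the sensitivity analysis has a standard error 5% or 14% larger if 25% or 50% of UVMMC participants enrol early (assumed). The primary model leaves calendar drift in, with the sensitivity analysis to reveal it, and the conclusion is more modest.
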